**Days 0-7: After the second vaccination:**

- The following data will be recorded on the memory aid form by the subjects each evening:
  - Oral temperature
  - Local reactions
  - General reactions
  - Concomitant medications given

**Days 1-3 and Days 8-10 after second vaccination:** Telephone and/or electronic communication

- An attempt of telephone and/or electronic communication will be made/sent between Days 1-3 and again on Days 8-10:
  - Appropriate data will be collected, and they will ensure the memory aid forms are being completed correctly
  - Any adverse events that have occurred will be collected
  - Questions the subject may have will be answered
  - Any concomitant medication will be recorded

**Visit 3: 28-42 Days after Visit 2**

- Solicited AEs/unsolicited AEs will be reviewed and recorded in through 7 days following vaccination #2
- Targeted physical examination will be conducted if indicated.
- Any concomitant medication will be recorded.
- Any new immunizations since last visit will be reviewed and recorded.
- Approximately 20-40 mL of blood will be collected for HAI and MN assays to influenza virus antigens, phenotypic B, and T cell responses, B and T cell specific influenza responses, CBC d/p, quantitative CD4+/CD8+/CD19+ levels, and quantitative serum IgM and IgG concentrations.
- A second blood draw will be obtained post-IVIG/SCIG if administered.
- Only during influenza season, a nasal swab will be obtained, regardless of symptoms.
- For the 2019/2020 enrollment season, subjects who are not able to return for visit 3 will have an arrangement for a blood draw to be done locally and shipped to the research team. Subjects will also be called and asked about their health and medication changes. Also, they will be asked to collect a nose swab and mail it to the research team.

### **Influenza Surveillance:**

Active surveillance for influenza-like symptoms will begin when influenza season starts at each site's community. Influenza season begins in the specific community, defined as in previous trials by identification of at least 2 positive respiratory tests for influenza, with at least 10% of diagnostic tests positive during 2 consecutive weeks in the local clinical or research laboratory. Enrollment will continue during influenza season with nasal swabs obtained at all main visits to document the occurrence of influenza virus detection both prior to and after vaccination.

Study staff will attempt to collect nasal swabs from patients who meet the ILI criteria during the entire study period.

When the flu season starts, the study staff will attempt to do a weekly telephone and/or electronic communication with the participants to detect and document any influenza like illness (ILI). Patients who meet the ILI criteria will be asked to collect a nasal swab and mail it back to the study site.

#### **ILI criteria: One of following criteria met:**

- **Fever:**  $\geq 38.3^{\circ}\text{C}$  ( $101^{\circ}\text{F}$ ); or
- **Two or more of any of the following:** respiratory symptoms (rhinorrhea, sinus congestion, post-nasal drip, shortness of breath, cough, wheezing, sputum production, sore throat, sneezing, watery eyes, ear pain, hoarseness); or systemic symptoms (myalgias and headache).

A nasal swab will be collected. If distance is an issue or if symptoms start on a weekend, subjects will be given PrimeStore MTM to take to their local pediatrician's office, or with proper instructions, home collection can be done, and arrangements will be made for specimens to be sent either to the local academic center or directly to Vanderbilt in Nashville, TN. Specimens should be collected within 7 days of onset of symptoms, ideally within 48 hours.

Note: For subjects who finish their visit 4 before the end of the flu season, influenza surveillance will continue until the end of the flu season at their site's community.

### **Visit 4: 180 Days $\pm$ 42 after Visit 2**

- Approximately 20-40mL of blood will be collected for HAI and MN assays to influenza virus antigens, phenotypic B, and T cell responses, B and T cell specific influenza responses, CBC d/p, quantitative CD4 $^{+}$ /CD8 $^{+}$ /CD19 $^{+}$  levels, and quantitative serum IgM and IgG concentrations.
- A second blood draw will be obtained post-IVIG/SCIG if administered.
- Only during influenza season, a nasal swab will be obtained, regardless of symptoms.
- For the 2019/2020 enrollment season, visit 4 will be optional and subjects who volunteer to participate will have the procedures outlined above.

### **Optional visits: 5-10 days after each vaccination**

- Only those subjects who volunteer, will return for a blood draw only.
- Approximately 20-40 mL of blood will be collected for B and T cells responses.
- If within the 8-10 days phone call window, this would replace the 8-10 day telephone and/or electronic communication.

Note: Data for proven clinical influenza infection will be collected during the study period and through June 30th.

### **15. Laboratory Procedures:**

- a. **Specimen Preparation, Handling, and Shipping:** Blood will be collected from a vein or from a central line from subjects. Study personnel or clinical research staff will collect the blood samples, label without personal identifiers, and deliver to the laboratory for preparation of serum and freezing of the sera until further testing and/or shipment to Sanofi laboratory for HAI and MN testing and B and T cell influenza-specific testing at Vanderbilt. Other clinical labs will be sent the local lab.
- b. **Hemagglutination Inhibition Assays (HAI):** Sera will be shipped to **Sanofi** laboratory for HAI testing. Sera will be initially diluted 1:10 per protocol. Pre-vaccination and post-vaccination sera will be analyzed simultaneously to minimize variability in the HAI assay. HAI titers will be determined for each influenza antigen included in QIV 2016-2017 or 2017-2018 or 2018-2019.
- c. **Neuraminidase Inhibition Assays (NAI):** Sera will be shipped to Vanderbilt for NAI testing and results will be compared to HAI. NAI testing will be done at [name] lab in Mt. Sinai.
- d. **Microneutralization assays:** Sera will be shipped to **Sanofi** laboratory for MN testing and results will be compared to HAI.
- e. **Influenza-specific B and T cell Responses and Immunophenotyping of B and T cells:** Samples will be collected at baseline, 5-10 days (optional) and 28-42 days after each vaccination and 180 days ( $\pm$ 42 days) after second vaccination. After ficoll separation, peripheral blood mononuclear cells (PBMC) will be cryopreserved for future analysis. Each site will do this locally and the off-sites will ship to **[name]** laboratory at Vanderbilt in Nashville, TN. This will ensure all time points from each individual can be evaluated simultaneously. We propose to study B and T cell responses to vaccination with mass cytometry technology (CyTOF), and functional assays such as *in-vitro* IL-21 production in response to vaccine antigen.
- f. **Nasal swabs:** a nasal swab will be collected by either using viral transport media or using PrimeStore MTM, which can be stored at room temperature until ready for shipment to Vanderbilt in Nashville, TN for PCR testing for influenza.

## 16. Specification of Safety Parameters:

Safety will be assessed by frequency, incidence and severity of AEs and SAEs solicited in-clinic and via memory aids, telephone and/or electronic communication conversations, concomitant medications, and periodic physical evaluations.

**Safety monitoring plan post 15 minute vaccination:** Either a nurse, NP, or LPN will administer the vaccine. The subject will wait at least 15 minutes to be observed by the research staff or clinical research staff. These individuals will be in a location that will have access to individuals with advanced cardiac life support skills.

## Methods and Timing for Assessing, Recording, and Analyzing Safety Parameters

### a. Adverse Events, Reactogenicity, Serious Adverse Events

The investigator is responsible for reporting:

- Any Grade 3 Adverse event that is not attributable to underlying disease for which the transplant was undertaken, **or** not attributable to GVHD, **or** not attributable to complications of immunosuppressive medications **and** are observed or reported through 7 days following vaccination, regardless of their relationship to study product.
- Any other AE will not be reported unless it meets the SAE criteria (see Section 16.f).

A physician, nurse, nurse practitioner, and/or physician's assistant will assess initial vaccine reactions for at least 15 minutes after vaccination. Subjects will be asked to record both solicited vaccine reactions

(reactogenicity) and any unsolicited AEs on a memory aid for 7+ days after each vaccination (Day 0 through Day 7). Study personnel will attempt to contact the subjects by telephone and/or electronic communication at 1 to 3 days and again 8-10 days after each vaccination to review any AEs and SAEs.

AEs and SAEs will be collected through 7 days following each vaccination. Adverse events will be followed until resolution or until considered stable. **Solicited injection site AEs** will include the following: pain, tenderness, erythema/redness, and swelling/induration (**Table 4**). **Solicited systemic AEs** will be collected for 7+ days post each vaccination and will include the following: fevers, fatigue/malaise, headache, nausea, body ache/myalgia, generally activity, and vomiting (**Table 5**).

**b. Definition of Adverse Event:**

**Adverse Event:** The International Conference on Harmonization (ICH) guideline E6 defines an AE as any untoward medical occurrence in a patient or clinical investigation subject administered a pharmaceutical product regardless of its causal relationship to the study treatment. An AE can therefore be any unfavorable and unintended sign (including an abnormal laboratory finding), symptom, or disease temporally related to the use of medicinal (investigational) product. The occurrence of an AE may come to the attention of study personnel during study visits and interviews or by a vaccine recipient presenting for medical care.

AEs must be graded for severity and relationship to study product (see below). Severity can be assessed by a licensed clinician (i.e., physician, nurse, nurse practitioner, physician's assistant). Relationship to study product can only be assessed by a clinician licensed to make medical diagnoses (i.e. physician, nurse practitioner, physician's assistant) listed on the Form FDA 1572.

Adverse events characterized as intermittent require documentation of onset and duration of each episode. The start and stop date of each reported AE will be recorded on the data collection forms and eCRF.

**c. Severity of Event:** AEs will be assessed by the clinician using a protocol defined grading system. For events not included in the protocol defined grading system, the following guidelines will be used to quantify severity:

- **Grade 1 -Mild:** events require minimal or no treatment and do not interfere with the patient's daily activities.
- **Grade 2 -Moderate:** events result in a low level of inconvenience or concern with the therapeutic measures. Moderate events may cause some interference with functioning.
- **Grade 3 -Severe:** events interrupt a patient's usual daily activity and may require systemic drug therapy or other treatment. Severe events are usually incapacitating **or Life-threatening**, i.e. any adverse drug experience that places the patient or subject, in the view of the investigator, at immediate risk of death from the reaction as it occurred. It does not include a reaction that had it occurred in a more severe form, might have caused death.

**d. Relationship to study products/vaccines:**

The investigator's assessment of the relationship of an AE to the study drug/vaccine is part of the documentation process, but it is not a factor in determining what is or is not reported in the study. If there is any doubt as to whether a clinical observation is an AE, the event should be reported. AEs must have their possible relationship to study vaccine assessed using the following terms: related or not related. In a clinical trial, the study product must always be suspect. To help assess, the following guidelines are used.

- **Related –** The event is temporally related to the administration of the study product and no other etiology explains the event.
- **Not Related –** The event is temporally independent of study product and/or the event appears to be explained by another etiology.

**Comparison of High vs. Standard Dose Flu Vaccine in Pediatric Stem Cell Transplant Recipients****DMID Protocol Number 16-0117****Protocol Version 8.0**

Date: 9/12/2019

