**e. Reactogenicity:**

Reactogenicity events are AEs that are known to occur with this type of vaccine. The following Toxicity Grading Scales will be used to grade local and systemic (both quantitative and subjective) reactions:

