## **h. Serious Adverse Event Detection and Reporting**

SAEs as defined in Section 16.f will be:

- Notified to the IND Sponsor/Lead PI ([name]), local site PI and/or Sub-Is and DMID Pharmacovigilance Group (PVG) within 24 hours of knowledge of the SAE.
- Assessed for severity and relationship by a licensed clinician listed on the FDA Form 1572 as the PI or a Sub-Investigator.
- Recorded on the appropriate SAE report form.
- Followed through resolution by a study physician.
- Reviewed by an Independent Safety Monitor (ISM), Data and Safety Monitoring Board (DSMB) (periodic review unless related), DMID, and IRB.
- SAEs related to the study vaccine that are unexpected and fatal or life-threatening will be reported to the FDA no later than 7 calendar days after SAE awareness.
- SAEs related to the study vaccine that are unexpected and serious (not fatal or life-threatening) are to be reported to the FDA no later than 15 calendar days after SAE awareness.
- All other SAEs will be submitted with the FDA Annual Report in summary form.
- All SAEs unexpected and deemed related to the study vaccine will be reported to Sanofi within 7-15 calendar days after SAE awareness.

SAEs occurring through 7 days following vaccination will also be reported to the local IRB within 1-2 calendar days as the team becomes aware of the SAE or per local IRB protocol/procedures.

Any AE that meets a protocol-defined serious criterion as defined in Section 16.f will be submitted immediately (within 24 hours of site awareness) on a SAE form to the DMID Pharmacovigilance Group, to the following address:

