### j. Halting Rules:

The ISM of each site, DMID, and DSMB will be provided safety data in order to advise on matters of safety, including halting the trial. The safety data will consist of immediate reactogenicity events (in the 15 minutes after vaccination), reactogenicity events recorded on the memory aid (each day for the week after vaccination), AEs, and SAEs. The data will be entered into ONCORE and/or REDCap and provided to the ISM, DMID, and DSMB for review. The presentation of the data will include whether any events contributing towards a halting rule have been met. The frequency of DSMB review will be defined in the charter.

The study will be halted (for further DSMB review/recommendation) if any of the following occur and it was not the result of trauma or accident, scheduled hospitalization or surgery, and is not attributable to disease relapse, GVHD, or and infection due to the immunosuppressed state of the patient. No new subjects will be enrolled if:

1. If one subject has an SAE and the adverse event is deemed severe within 7 days of vaccine that is determined to be related to the study vaccine by the site PI in consultation with the site ISM and the study PI, no new subjects will be enrolled. The SAEs will be reviewed by the DSMB for the relationship with the study vaccine and further discussed with DMID to determine continuation of the study.
2. If four or more subjects have the same Grade 3 event in any reactogenicity category (excluding grade 3 redness/ induration size or grade 3 fever) that is determined to be study vaccine-related, no new subjects will be enrolled. The AEs will be reviewed by the DSMB for the relationship with the study vaccine. For 2019-20, based on safety data from the previous years, the number of subjects will be increased to eight prior to halting.
3. 3 or more subjects have urticaria considered to be study vaccine-related.
4. 1 or more subjects have intramuscular injection-site ulceration, abscess, or necrosis.
5. 1 or more subjects have laryngospasm, bronchospasm or systemic anaphylaxis within 24 hours of administration of study vaccine.
6. 1 or more subjects have acute weakness of limbs or cranial nerve innervated muscles.
7. Any death occurring within the first 7 days following administration of study vaccine.

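### Protocol 16.d directs a Not Related call whenever another cause appears to explain an event, which can blunt halting rules 1 to 3 and the FDA and manufacturer reports

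*Protocol*

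**What the plan says.** Protocol section 16.d allows a binary judgement only: "AEs must have their possible relationship to study vaccine assessed using the following terms: related or not related". It states a principle, "In a clinical trial, the study product must always be suspect", and says that the causality assessment does not decide what is reported within the study. It then offers two guideline definitions.

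- Related: "The event is temporally related to the administration of the study product and no other etiology explains the event".
- The second term, Not Related, is met when the timing is unconnected with the vaccine, and/or when "the event appears to be explained by another etiology".

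Section 16.e introduces the solicited reactions with the statement "Reactogenicity events are AEs that are known to occur with this type of vaccine".

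The term is then used as a condition elsewhere in the protocol.

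- **Section 16.j.** Halting rule 1 (one severe SAE within 7 days), rule 2 (four or more subjects with the same Grade 3 reactogenicity event, eight for 2019-20) and rule 3 (three or more with urticaria) each need a relatedness finding. Rule 2 counts an event "that is determined to be study vaccine-related, no new subjects will be enrolled".
- **Section 16.h.** "SAEs related to the study vaccine that are unexpected and fatal or life-threatening will be reported to the FDA" within 7 days, and other serious, unexpected, related SAEs within 15 days. The manufacturer report has the same condition. All remaining SAEs reach the FDA in the annual summary. DSMB review of an SAE is periodic unless the SAE is related.

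**The concern.** The two terms carry unequal burdens. An apparent alternative is enough for Not Related, whereas Related needs the absence of any explaining alternative. Because the Not Related definition joins its two limbs with and/or, close timing does not rescue an event that has another apparent cause. There is no intermediate category, and no place for an event to which both the vaccine and another condition contributed.

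The children are 3 to 35 months past allogeneic transplant, and stable GVHD is allowed at entry. Fatigue, headache, nausea, vomiting and myalgia are solicited as known vaccine reactions, and they are also the events for which another explanation is easiest to find in such children. If some true vaccine reactions are called Not Related for that reason, the relatedness-dependent halting rules and reports become less sensitive.

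**Working it through.** **Tracing the term.**

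| Provision | Depends on Related? |
|---|---|
| 16.j halting rules 1, 2, 3 | Yes |
| 16.j halting rules 4 to 7 | No |
| 16.h FDA 7- and 15-day reports | Yes |
| 16.h manufacturer report | Yes |
| 16.h DSMB review of SAEs outside the periodic cycle | Yes |
| 16.h 24-hour notice to the sponsor and DMID | No, covers every protocol-defined SAE |
| Protocol 17.c and SAP 6.1 AE summaries | No |

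The statement in 16.d that relationship does not decide what is reported is therefore true of data capture and of the 24-hour notice. It does not hold for the FDA and manufacturer reports in 16.h.

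**A second filter.** The preamble to 16.j already sets aside events attributable to relapse, GVHD or infection from immunosuppression. The note to 16.f sets aside SAEs attributable to the underlying disease, GVHD or complications of immunosuppressive drugs. The 16.d definition acts on what remains.

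**Illustrative size.** The documents state no operating characteristic for the halting rules, so there is no plan figure to reproduce. Inputs:

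- n = 200 subjects (Protocol 17.a). Rule 2 counts subjects without restricting to one arm.
- Threshold r = 4, or 8 for 2019-20, for rule 2; 3 for rule 3; 1 for rule 1 (Protocol 16.j).
- p, the true per-subject rate of the vaccine-caused event: an assumption.
- s, the share of those events called Related: an assumption.

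With q = p × s,

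P(X ≥ r) = 1 − Σ(k = 0 to r−1) C(n,k) q^k (1−q)^(n−k).

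Rule 2, r = 4, p = 3%:

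- s = 1, q = 0.03: 1 − (0.0023 + 0.0140 + 0.0430 + 0.0879) = 0.853.
- s = 0.5, q = 0.015: 1 − (0.0487 + 0.1482 + 0.2246 + 0.2257) = 0.353.

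| Rule, threshold | p | s = 1 | s = 0.75 | s = 0.5 | s = 0.25 |
|---|---|---|---|---|---|
| 2, four subjects | 2% | 57% | 35% | 14% | 2% |
| 2, four subjects | 3% | 85% | 66% | 35% | 6.5% |
| 2, four subjects | 5% | 99% | 94% | 74% | 24% |
| 2, eight subjects | 5% | 79% | 48% | 13% | 0.4% |
| 3, three subjects | 2% | 76% | 58% | 32% | 8% |
| 1, one subject | 1% | 87% | 78% | 63% | 39% |

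At the threshold of eight with p = 6%, q is 0.06 when s = 1 and 0.03 when s = 0.5, and the chance falls from 92% to 25%. The 2019-20 season takes repeaters only, so 200 overstates the number at risk under that threshold.

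These figures treat p as a per-subject rate over both doses, and ignore staged enrolment and what the DSMB might do along the way.

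**The case against.** **The wording can be read more kindly.** The definitions are offered as guidelines, and they speak of another etiology that explains or appears to explain the event, not one that is merely conceivable. Read as related unless something else accounts for it, they can be squared with the lead-in. A reader might infer that nearly any reaction in these children becomes Not Related. The documents do not support that: they give no misclassification rate, relapse is excluded, GVHD must be stable for 4 weeks at entry, fever or recent acute illness delays vaccination, and conditions present at screening are baseline unless they worsen. Injection-site pain and tenderness also count under rule 2 and seldom have another cause. This part of the objection stands and limits the point.

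**Safeguards exist.** Every protocol-defined SAE goes to the sponsor and DMID within 24 hours. The independent safety monitor at each site reviews all SAEs, and rule 1 causality is settled with that monitor and the study PI. The DSMB sees safety and reactogenicity data every six months and may see them by arm. DMID can suspend the trial. These soften the consequence, but none changes the definition that triggers rules 1 to 3 or the FDA timelines.

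**Other filters do some of the work.** The exclusions in 16.f and in the 16.j preamble would still remove events attributed to GVHD or infection. That is correct, and rewording 16.d alone would not restore them.

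**The change comes late.** Version 8.0 is dated September 2019, after the three primary enrolment seasons, and the threshold of eight was set from safety data of earlier years. A new definition would weaken comparison with those years. This is a real cost, and it can be managed by recording the change.

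**Conclusion.** The point holds as an internal inconsistency with a limited safety consequence. The 16.d definitions direct a Not Related call when another cause appears to explain an event, against their own lead-in, and halting rules 1 to 3, the FDA and manufacturer reports and non-periodic DSMB review of SAEs turn on that call. The exposure lies mainly in fatigue, headache, nausea, vomiting and myalgia.

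The loss of sensitivity could be large or small. If half of true reactions were called Not Related, the chance of reaching four under rule 2 would fall from 85% to 35% at an assumed 3% rate in 200 subjects, but only from 99% to 74% at 5%. Both the rate and the share are assumptions.

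Two stronger conclusions that a reader might draw do not follow. The first is that the final safety tables would be biased low: neither Protocol 17.c nor SAP 6.1 plans a table restricted to related events. The second is that such events escape expedited reporting altogether: the 24-hour SAE notification does not depend on causality.

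**What to change.** Reword the two definitions in 16.d to agree with their lead-in. Related should cover a reasonable possibility that the vaccine caused or contributed to the event, even if another cause is also possible. Not Related should be kept for events that are temporally independent, or for which another cause is established and a vaccine contribution is not reasonably possible.

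Then reconcile 16.d with the SAE note in 16.f, the reporting conditions in 16.h and the preamble and rules in 16.j, so that it is clear which attribution test applies where. Also limit the 16.d statement about reporting to what it actually covers. How solicited reactions count towards halting, and the halting thresholds, are for the sponsor and DSMB to settle.

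The cost is two definitions and a training note to sites. More events would be classed as related, with somewhat more FDA and manufacturer reports and DSMB reviews. The definition would differ between seasons, which should be noted wherever 2019-20 causality data are compared with earlier years.
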